NCT03226769

Study ID: OCUN-023

Title: Prospective, Open-Label, Randomized, Proof of Concept Study Exploring Application of TrueTear™ for the Treatment of Meibomian Gland Disease

Protocol Date: 01 Jun 2017

ALLERGAN CONFIDENTIAL

The following contains confidential, proprietary information
which is the property of Allergan

Prospective, Open-Label, Randomized, Proof of Concept Study Exploring Application of TrueTear™ for the Treatment of Meibomian Gland Disease

[figure not shown]
Protocol Number: OCUN-023

Original Protocol: June 1, 2017

Device Name: TrueTear

Sponsor: Allergan, Inc.

[REDACTED]

SYNOPSIS

Protocol Title:	Prospective, Open-Label, Randomized, Proof of Concept Study Exploring Application of TrueTear™ for the Treatment of Meibomian Gland Disease
Protocol Number:	OCUN-023
Study Device(s):	TrueTear
Study Objective:	The primary objective of this study is to compare the safety and efficacy of TrueTear to standardized moist heat compress (Thermalon® Dry Eye Compress) for the treatment of Meibomian Gland Disease (MGD)
Overall Study Design	
Structure:	Prospective, open-label, randomized (1:1), parallel two arm design
Duration:	An individual participant’s participation is expected to last approximately 44 days
Controls:	Thermalon Dry Eye Compress [REDACTED] [REDACTED]
Device Regimen:	TrueTear: 
 • Initial in-office application of approximately 8 minutes duration at Visit 2 [REDACTED] • Second in-office application of approximately 3 minutes at Visit 3 [REDACTED] • Daily use of TrueTear per Patient Guide with assessments at Visit 3 ([REDACTED], Visit 4 [REDACTED] and Visit 5 ([REDACTED)
Control Regimen:	Thermalon Dry Eye Compress: 
 • In-office applications at Visit 2 ([REDACTED] and Visit 3 [REDACTED] and daily use as per label instructions with assessments at Visit 3 [REDACTED] Visit 4 [REDACTED] and Visit 5 ([REDACTED)
[REDACTED]	[REDACTED] [REDACTED] [REDACTED] [REDACTED] [REDACTED] [REDACTED]

participants.

General Statistical Methods

Statistical analyses will use a two-tailed test and will be evaluated at an α of 0.05 unless otherwise specified. The mean, standard deviation (SD), median, minimum and maximum will be presented for continuous variables such as participant age. For categorical variables, such as sex, the number for each category, the total number evaluated, and the percentage will be presented.

[REDACTED]

[REDACTED]

1.0 INTRODUCTION

1.1 Background

Meibomian gland disease (MGD) is a chronic, diffuse abnormality of the meibomian glands, commonly characterized by terminal duct obstruction and/or qualitative/quantitative changes in glandular secretion.¹ MGD is a common eyelid disorder that has widespread prevalence of 37% to 47% in the United States (US) alone.² The incidence of MGD has been found to increase with age³⁻⁹ and is markedly higher in Asian populations (46.2% to 69.3%).¹⁰⁻¹² MGD may result in alteration of the tear film, symptoms of eye irritation, clinically apparent inflammation, and ocular surface disease.¹³ Combined, these manifestations afflict millions of people worldwide, with more than 10 million in the US alone.^{2,13}

Current recommendations for the management and treatment of MGD include: 1) lid-heating, massage, and cleaning, 2) topical antibiotic and/or topical steroids, 3) systemic anti-inflammatory antibiotics (e.g., tetracycline), 4) lubricants as adjunctive treatment, 5) LipiFlow® Thermal Pulsation System, 6) meibomian gland probing and 7) meibomian gland expression. Lid warming, lid hygiene, and lubricants are often found to be suboptimal / only partially effective.² Meibomian gland probing and expression can lead to patient discomfort and/or damage to the lid margin. Topical antibiotic and/or an antibiotic-steroid combination are prescribed for acute exacerbated cases or for anterior blepharitis, but are short-term and may not address the underlying cause(s) of MGD. Systemic antibiotics may lead to systemic side effects including gastrointestinal disturbance (e.g., from tetracyclines). Therefore, there remains a need for new treatment strategies targeting the treatment of MGD.

1.2 Rationale

The nasolacrimal reflex is a well-established pathway by which nasal stimuli promote both resting basal¹⁴ and bolus tear secretion. The reflex plays a functional role in expelling foreign bodies or irritants from the nose by secreting tears into the nasal cavity via the nasolacrimal duct upon stimulation by the irritant.

Reflex activation of the lacrimal glands is also one of the body's primary compensatory mechanisms for addressing ocular surface dryness. Unfortunately, over time, an arid environment and resulting inflammation results in damage to the afferent nerves innervating the cornea, compromising the reflex response and ultimately leading to an even drier ocular surface.

Studies have demonstrated that intranasal stimulation via use of the TrueTear application results in a statistically significant increase in tear production measured by the Schirmer test.^{15,16} To date, however, little is known regarding the role intranasal neurostimulation may have on secretion of meibum. The meibomian glands are not innervated directly¹⁷ and the mechanism by which meibum that is secreted into the glands and expressed onto the eyelids is a two-stage process. First meibum is continually secreted by sebaceous cells into the meibomian glands for storage prior to expression.^{18,19} Second, meibum expression is achieved through coordinated muscular activity (which can be initiated by numerous stimuli such as blinking), of the orbicularis muscle (the eyelid) contracting, and Riolan's muscle (a sphincter at the orifice of the glands just below the lid margin) relaxing. The innervation to the muscoli orbicularis and

Riolan's is provided by the facial nerve (cranial nerve CN-VII) whose fibers transmit action potentials to contract said musculi upon neural activity in the superior salivatory nucleus in the brainstem.^{18,20} This nucleus is responsible for the secretion of tears and tear components and shows neural activity when sensory nerve endings of the anterior ethmoidal nerve, a sub-branch of the trigeminal nerve, are stimulated.²¹⁻²³ The TrueTear stimulates the anterior ethmoidal nerve inside the nose, thereby increasing neural activity in the superior salivary nucleus, which in turn drives action potentials on the facial nerve to the lacrimal gland as well as provides the signals for coordinated activation of the orbicularis and the Riolan's muscles, thereby expressing meibum from the meibomian glands. As such, there is reason to believe that meibum expression may be achieved following stimulation of anterior ethmoidal afferences inside the nose.

A clinical study conducted by the Sponsor measuring meibomian gland activity and tear film lipid layer thickness stimulated with use of TrueTear supports this assumption. Specifically, in this study, evidence of increased meibomian gland secretion activity and increased tear film lipid layer thickness was measured following a single use of TrueTear relative to both pre-application of TrueTear and an extranasal control.²⁴ It is thus of interest to the Sponsor to investigate the effectiveness of TrueTear as a potential novel treatment strategy for MGD.

2.0 STUDY OBJECTIVES

The primary objective of this study is to compare the safety and efficacy of TrueTear (intranasal tear neurostimulation) to standardized moist heat compress (Thermalon Dry Eye Compress) for the treatment of Meibomian Gland Disease (MGD).

[figure not shown]
3.0 CLINICAL HYPOTHESES

[figure not shown]
Thirty days of TrueTear application provides efficacious treatment of MGD compared to moist heat compress control as measured by signs and/or symptoms of MGD.

4.0 OVERALL STUDY DESIGN

This is a prospective, randomized, parallel two-arm study conducted at up to two sites, designed to characterize the effectiveness of TrueTear on the signs and symptoms of MGD. Approximately 70 male and female participants at least 22 years of age with a participant-reported history of dry eye or MGD and meeting all other study eligibility criteria will be randomized in a 1:1 ratio to either the TrueTear or moist heat compress control treatment groups. Following the initial application of treatment in clinic at Day 0, participants will apply the randomized treatment for approximately 30 days.

5.0 STUDY POPULATION

5.1 Number of Participants

It is estimated that approximately 70 participants will be enrolled at up to two sites in the US to complete approximately 60 participants.

Participants will be randomized in a 1:1 ratio to one of two possible treatment groups:

- TrueTear
- Thermalon Dry Eye Compress (moist heat compress)

5.2 Study Population Characteristics

All participants should meet all inclusion criteria and none of the exclusion criteria.

5.3 Inclusion Criteria

Participants should:

[figure not shown]
1. Be twenty-two (22) years of age or older at the Screening Visit

2. At the Screening and Baseline Visits, have a Standard Patient Evaluation for Dryness (SPEED) [REDACTED]
3. In at least one eye, meet all of the following objective measures in the same eye:
 - A basal Schirmer test [REDACTED]
 - [REDACTED]
 - [REDACTED]
 - Tear film breakup time (TBUT) \geq [REDACTED]
4. Have used an artificial tear product, lid hygiene [REDACTED]; omega-3 supplementation; antibiotics [REDACTED] for the treatment of dry eye disease or meibomian gland disease within one year of the Screening Visit
 - [REDACTED]
 - [REDACTED]
 - [REDACTED]

[figure not shown]
5.4 Exclusion Criteria

Participants should not:

1. Have chronic or recurrent epistaxis, coagulation disorders or other conditions that, in the opinion of the Investigator, may lead to clinically significant risk of increased bleeding
2. Have had nasal or sinus surgery (including history of application of nasal cautery) or significant trauma to these areas
3. Have a vascularized polyp, severely deviated septum or severe nasal airway obstruction as confirmed by intranasal examination performed at the Screening Visit
4. Have had any intraocular surgery (such as cataract surgery), extraocular surgery ([REDACTED]) in either eye within three months of the Screening Visit or refractive surgery [REDACTED] within twelve months of the Screening Visit
 - [REDACTED]
 - [REDACTED]

16. Have a cardiac demand pacemaker, implanted defibrillator, or other active implanted metallic or active implanted electronic device in the head

- [REDACTED]
 - [REDACTED]
 - [REDACTED]
 - [REDACTED]
 - [REDACTED]
- [REDACTED]
- [REDACTED]
- [REDACTED]
- [REDACTED]

5.5 Inclusion/Exclusion Exceptions

The Investigator has the right to exclude a potential participant's enrollment in the study if s/he deems it in the best interest of the participant. Reasons for exclusion on this basis will be recorded.

5.6 Discontinuation Criteria (if applicable)

Participants are free to discontinue their participation in this study at any time and for any reason, specified or unspecified, without prejudice. In addition, the Investigator may decide to discontinue a participant from the study for safety reasons or when it is in the best interest of the participant. No constraints will be placed on ordinary patient management.

Reasons for participant withdrawal may include but are not limited to the following:

- Either at the Investigator's request, for safety reasons (e.g., serious or severe AE), or at the participant's request
- Non-compliance (e.g., failure to follow application instructions, missing visits, using prohibited medications)
- When a concomitant therapy likely to interfere with the results of the study is reported or required by the participant; the Investigator will report all such information on the source documents/case report forms (CRFs) and decide, in conjunction with the Sponsor, whether the participant is to be withdrawn
- Sound medical reason
- A confirmed positive pregnancy test at any time during the study
- When a participant is lost to follow-up. The Investigator (or designee) will make repeated attempts to reach the participant by telephone, email and/or letter before considering the participant as lost to follow-up. These actions will be documented and recorded on the End of Study CRF. Copies of follow-up letters, if any, should be maintained in the Investigator's file.
- When a participant is erroneously admitted into the study or does not meet the eligibility criteria

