8.2 Masking

Because the two devices are dissimilar and administered in very different ways, it will not be possible to mask the participant or the Investigator to the intervention assignment. As a means of minimizing bias where feasible, de-identified videos from the Tearscope assessment (lipid layer thickness) will be graded using the Guillon scale in a masked fashion.

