8.3 Participant Training, Dispensing and Home Use of TrueTear

At Visit 2 (Day 0), participants randomized to the TrueTear application group will be provided a TrueTear device and disposable tips to take home with them and use daily. Participants will be instructed to use the device as described in the Patient Guide. They will receive training to perform intranasal neurostimulation and will receive a copy of the Patient Guide.

For the device application, participants will be told to turn on the unit by holding down the + button for approximately two seconds. There are five stimulation intensity levels and participants may adjust the level by pressing the + or – buttons to obtain a gentle tingling sensation. They will be instructed to fully insert the tips of the TrueTear into both nostrils simultaneously towards the top and front of the nose (as in Figure 2). Participants will be told they can cease stimulation by holding down the – button for approximately two seconds on the base unit or by withdrawing the tips from the nostrils. Participants will be instructed to replace the Tips with a new one if they do not feel any sensation.

For the initial in-office device application at Visit 2 (Day 0), each participant will be told that the application will take place for approximately eight minutes and that the entire procedure will occur while the participant is seated and positioned in a slit lamp to allow for simultaneous viewing of meibomian gland activity in the lower lid and for collection of lid and tear film temperature data.

At Visit 3 (Day 7), prior to in-office application and evaluation of tear secretion, trained clinical personnel will review procedures for the proper use of the device (e.g., correct positioning intranasally, frequency and duration of use, daily replacement and disposal of tips, etc.) with participants. As the device internally records the frequency and duration of device use, study staff may review this information with participants. Participants will be told that the in-office application of TrueTear at this visit should last for approximately three minutes.

Figure 2 Use of TrueTear

(L) Starting position and (R) Correct application position by inserting the disposable tips fully into the nasal cavity and to the front of the nose.

Note: Sponsor representatives may be present at visits to assist in training participants on the use of the device.

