5.0 PATIENT POPULATIONS

5.1 INTENT-TO-TREAT POPULATION

The Intent-to-Treat (ITT) Population will consist of all randomized patients.

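### Protocol section 5.6 permits withdrawal from the study itself for non-compliance or ineligibility in an open-label trial, and no readable text keeps those participants in follow-up, so Day 30 data can be lost informatively

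*Protocol*

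**What the plan says.** Protocol section 5.6 gives a power to end study participation: "the Investigator may decide to discontinue a participant from the study for safety reasons or when it is in the best interest of the participant". It then lists grounds under an open heading, "Reasons for participant withdrawal may include but are not limited to the following". Two of them matter here: "Non-compliance (e.g., failure to follow application instructions, missing visits, using prohibited medications" and "When a participant is erroneously admitted into the study or does not meet the eligibility criteria". Neither of these two items says who decides. The Sponsor appears in one other item, on concomitant therapy likely to interfere with the results, where the Investigator is to "decide, in conjunction with the Sponsor, whether the participant is to be withdrawn".

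Section 8.2 states that "it will not be possible to mask the participant or the Investigator to the intervention assignment"; only the grading of Tearscope videos is masked. Section 8.8 counts as completers only those who were not discontinued and who completed Day 30.

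Use of the assigned treatment is recorded differently in the two arms. For TrueTear, section 8.3 says: "As the device internally records the frequency and duration of device use, study staff may review this information with participants". For the compress, section 8.4 relies on a diary that the participant fills in.

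Protocol section 11.2 sets a two-sided null hypothesis of no difference between the devices, and the synopsis sets alpha at 0.05. SAP section 5.1 says: "The Intent-to-Treat (ITT) Population will consist of all randomized patients".

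**The concern.** The listed grounds end participation in the study, and the readable text offers no separate status of being off the device but still followed. Non-compliance, a missed visit and use of a prohibited medication during treatment all arise after randomisation, and the Investigator by then knows the arm. Ineligibility discovered late is in the same position.

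If participants who leave on these grounds differ in outcome from those who stay, and if they leave unevenly between arms, the Day 30 comparison is no longer protected by randomisation. An ITT population of all randomised patients does not repair this, because an analysis rule can only model values that were never collected.

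There is one documented route to imbalance. A device log makes failure to follow application instructions easier to see in the TrueTear arm than a diary does in the compress arm.

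**Working it through.** **Inputs from the documents.** About 70 enrolled to give about 60 completed (Protocol 11.1, SAP 12.0); 1:1 allocation, so 35 per arm (Protocol 5.1); two-sided alpha 0.05 (synopsis). No effect size, SD or power is given, so outcomes are in SD units.

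**The plan's own figure.** Implied non-completion is 10/70 = 14.3%, and 60/(1 − 10/70) = 70. This is only a consistency check, since the rate is derived from the same two numbers; a 15% allowance, 60/0.85 = 70.6, fits as well. The ten cover every reason for leaving.

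**Assumptions.** All ten non-completers are withdrawals of the kind at issue, there is no true difference between arms, and completers are compared by t-test. The split between arms and the link between compliance and outcome are not in the documents, so both are varied.

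**Check 1, simulation.** Each arm has 35 standard normal outcomes. Each participant also has a compliance score with correlation rho to the outcome, and the lowest scorers are withdrawn. There were 40,000 replicates per scenario.

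| Withdrawals by arm | rho | Bias (SD) | Type I error |
|---|---|---|---|
| 5/5 | 0 | 0.00 | 5.0% |
| 5/5 | 0.3 | 0.00 | 5.3% |
| 5/5 | 0.5 | 0.00 | 5.7% |
| 7/3 | 0 | 0.00 | 5.1% |
| 7/3 | 0.3 | 0.05 | 5.6% |
| 7/3 | 0.5 | 0.09 | 7.2% |
| 10/0 | 0 | 0.00 | 4.9% |
| 10/0 | 0.3 | 0.14 | 8.3% |
| 10/0 | 0.5 | 0.23 | 15.1% |

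At rho = 1 the 10/0 split gives 0.46 SD and 49%. That needs compliance to track outcome perfectly, so it is a mathematical limit and not a scenario.

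**Check 2, fixed difference.** Suppose withdrawn participants are d SD worse than completers, with d from 0.5 to 1.0. If one arm has a net excess of k withdrawals, bias = (k/35) × d. The rejection rate comes from the noncentral t with noncentrality bias/SE.

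- 10/0: k = 10, so bias = (10/35) × 0.5 = 0.143 to (10/35) × 1.0 = 0.286 SD. SE = √(1/25 + 1/35) = 0.262. Noncentrality is 0.55 to 1.09 on 58 df, and rejection is 8.4% to 18.9%.
- 7/3: k = 4, so bias = 0.057 to 0.114 SD. SE = √(1/28 + 1/32) = 0.259. Rejection is 5.5% to 7.2%, the same error range as the simulation with a slightly larger bias.

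**Scale.** With 30 completers per arm, SE = √(2/30) = 0.258 SD. The difference detectable with 80% power is (1.960 + 0.842) × 0.258 = 0.72 SD.

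Material bias therefore needs withdrawals that are both related to outcome and unevenly split.

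**The case against.** The strongest reply is that section 5.6 is permissive. It sets no compliance threshold and mandates no withdrawal. It may also be applied rarely: an excess of two such withdrawals in one arm gives a bias of (2/35) × 0.5 to 1.0 = 0.03 to 0.06 SD and an error of 5.1% to 5.5%; an excess of three gives 5.3% to 6.2% (SE 0.258 SD). That stands as to size. It does not remove the point, because discretion without a rule, exercised with the arm known, can vary by arm.

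Redaction limits what can be said. SAP 9.1 names no effectiveness measure and the text after 9.2 is blacked out. The visible uses of ITT are disposition and baseline tables. An early-exit procedure could sit in the redacted text between Protocol 8.5 and 8.8. So the Day 30 population and missing-data method cannot be called absent, and the completers-only comparison used above is an assumption that ignores any use of Day 7 and Day 14 data.

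Some of the risk is already visible to a reader of the results. SAP 6.0 tabulates discontinuation reasons by arm, and SAP 7.0 lists eligibility and procedural deviations. This would reveal an imbalance but would not recover the data.

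A reader might also infer three things that the documents do not support:

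- **That the Sponsor shares in all these withdrawals.** Its role is written only for interfering concomitant therapy, and whether the Sponsor is masked is not stated.
- **That the log-versus-diary difference affects every ground.** It bears on failure to follow application instructions. Nothing readable suggests that missed visits, prohibited medication or ineligibility are recorded differently by arm. The log review in 8.3 is described as part of retraining, not as a trigger for withdrawal.
- **That every eligibility withdrawal follows randomisation.** That item could also cover failures found at Screening or at the Visit 2 check.

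**Conclusion.** The point holds as a risk that the readable protocol permits, not as a demonstrated loss. Section 5.6 allows randomised participants to leave the study on grounds that may relate to outcome, the Investigator knows the arm, and no readable provision keeps them in follow-up. That sits badly with a between-arm hypothesis and an all-randomised ITT definition.

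If all ten expected non-completers were such withdrawals, a 7/3 split would give a bias of about 0.05 to 0.09 SD and a type I error of about 6% to 7% (rho 0.3 to 0.5). The extreme 10/0 split would give about 8% to 19% across the two calculations. Balanced withdrawals, or withdrawals unrelated to outcome, give essentially no bias.

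It is tempting to conclude that the comparison is tilted towards TrueTear. That would need non-users to do worse and to be removed mainly from that arm, and the documents show neither. Nor should 19% be read as the expected error: it needs all ten from one arm and a 1.0 SD deficit together.

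A precision gain of about 7% (SE from 0.258 to √(2/35) = 0.239 SD) would likewise need all 70 to be observed, although consent withdrawal and loss to follow-up will remain. Keeping two more per arm gives √(2/32) = 0.250 SD, a gain of about 3%.

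**What to change.** Amend Protocol section 5.6, and 8.8 to match, so that stopping the device and leaving the study are separate events. State that non-compliance, a missed visit, use of a prohibited medication, or ineligibility found after randomisation does not by itself end follow-up. Such participants are asked to attend the remaining scheduled assessments through Day 30 unless they withdraw consent or cannot be contacted. Record each event as a deviation and analyse the collected data in the randomised arm. Where someone is still withdrawn from the study, report it by arm, reason and who made the decision.

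The edit concerns follow-up only. It proposes no rule on device use or stopping, including for participants found ineligible.

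The cost is a short amendment and a few more attendances at visits already scheduled. The downside is that including non-users dilutes the estimated effect slightly, which is inherent in comparing everyone as randomised.
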